## **2. SYNOPSIS**

---

Financial Disclosure Information for U.S. FDA Submission  
to be Obtained?

Yes       X No

---

Investigational Products:      ALLEVYN LIFE Non-Bordered

Product Used in Study:      ALLEVYN LIFE Non-Bordered is a borderless, multilayer foam dressing with a silicone adhesive.

Active Ingredients:      NA

---

Objective(s):      The primary objective is to estimate the effect of treatment with Allevyn Life Non-Bordered (ALNB) on Health-Related Quality of Life (HRQoL) in subjects with chronic ulcers, measured using the Cardiff Wound Impact Schedule Physical Symptoms and Daily Living (CWIS-PSDL) scale, compared to subjects receiving SC alone, over a six week treatment period.

Secondary objectives of this study are:

- 1) To estimate the effects of treatment with ALNB, when compared with SC alone, on:
  - a. HRQoL measured by the CWIS-PSDL scale at three and twelve weeks, and CWIS well-being (WB), social life (SL); global quality of life (GQ); and satisfaction with quality of

life (SQ) scales; at three, six, and twelve weeks

- b. Ulcer progression (including undermining, necrotic tissue type and amount, exudate type and amount, skin color surrounding the wound, granulation tissue, epithelialization, condition of peri-wound, ulcer dimensions and healing status) at three, six, and twelve weeks
- 2) Health care resource use related to the reference ulcer (including number and cost of dressings used, time in hospital, number and cost of additional treatments, procedures, and investigations) over twelve weeks

The exploratory objectives of this study are to compare differences between ALNB and SC in dressing performance (including wear time, leakage, odor control, and absorption under compression) and usability (including comfort and ease of application/removal together with associated pain) at three, six, and twelve weeks.

Study Population:

Adults aged 18 years and older with moderate to highly exuding chronic ulcers.

Structure: Parallel Group

Duration of Treatment: Up to 12 weeks

Duration of Assessment: Up to 12 weeks

Multi-Center:  Yes Number of Centers: Up to 6  
 No

Blinding:	 None	 Subject-Blind
		 Double-Blind

Randomization:	X	Yes	Group Assignment Ratio: 5:3 in favor of ALNB (ALNB n = 25; SC n = 15)
		No	Stratified by wound type: diabetic foot ulcer (DFU), leg ulcer (LU) and pressure ulcer (PU).

### Concurrent Comparator: Standard Care (SC)

Estimated Total Sample Size: A minimum of 40 randomized subjects.

## Statistical Rationale

Provided:  X  No

Subject Population: Adult subjects ( $\geq 18$  years of age) presenting with a moderate

to highly exuding chronic ulcer that, in the opinion of the Investigator, would benefit from a protective dressing but does not require topical antimicrobial treatment. Chronic ulcers will include leg ulcers (LU) of any etiology, pressure ulcers (PU), and nonischemic diabetic foot ulcers (DFU).

---

Variable(s): PRIMARY:

The change in CWIS-PSDL scale score between baseline and six weeks in each treatment group.

KEY  
SECONDARY:

Subject-reported HRQoL variables (measured using the CWIS) to be compared between groups for change over three, six, and twelve weeks for the domains of CWIS-SL, CWIS-WB, and CWIS-GQ and at 3 and 12 weeks for CWIS-PSDL.

SECONDARY

Ulcer progression variables to be compared between groups at three, six, and twelve weeks including:

- Modified Bates-Jensen Wound Assessment Tool
  - Undermining
  - Necrotic tissue type
  - Necrotic tissue amount
  - Exudate type
  - Exudate amount
  - Skin color surrounding the wound
  - Granulation tissue
  - Epithelialization
- Condition of peri-wound
- Ulcer dimensions
- Ulcer healed status

Healthcare resource use variables (to be compared between groups over the entire twelve week study period) including:

- Dressings used (number and type for both primary and secondary dressings), including use of compression therapy
- Healthcare consultations (number and type)
- Time spent by health care providers (HCP) in treating/caring for reference ulcer
- Time in hospital (nights spent as an inpatient due to reference ulcer)
- Interventions/procedures related to the reference ulcer (number and type), including debridement of the ulcer (curette, scissors, scalpel, forceps, other)
- Concomitant therapies/treatments (number and type) used on the reference ulcer

**EXPLORATORY:** Further exploratory data will be gathered for dressing performance and usability/acceptability and compared between groups, where appropriate. Relevant variables will include:

- Dressing wear time (days)
- Dressing leakage (HCP-assessed)
- Ease of dressing application/removal (HCP-assessed)
- Dressing use (whether dressing was cut and adherence following repositioning)
- Odor control of dressing (HCP-assessed)
- Absorption under compression (HCP-assessed for subjects with LU requiring compression).
- Reason for dressing change (HCP-assessed)
- Pain on dressing removal (subject-reported)
- Comfort during wear (subject-reported)

**SAFETY:** Safety data will be gathered throughout the twelve weeks of the study, including:

- Adverse events
- Device deficiencies

### 3.4 LIST OF ABBREVIATIONS

Abbreviation	Definition
ABI	Ankle Brachial Index
ADE	Adverse Device Effect(s)
AE	Adverse Event(s)
ALNB	ALLEVYN LIFE Non-Bordered
ASADE	Anticipated Serious Adverse Device Effect(s)
cm	centimeter
CWIS	Cardiff Wound Impact Schedule
DevD	Device Deficiency(ies)
DFU	Diabetic Foot Ulcer
eCRF	Electronic Case Report Form
FAS	Full Analysis Set
FDA	Food and Drug Administration
GCP	Good Clinical Practice
GQ	Global Quality of Life
HCP	Health Care Provider
HRQoL	Health-Related Quality of Life
IAD	Incontinence-Associated Dermatitis
IRB	Independent Ethics Committee
IFU	Instructions for Use
IRB	Institutional Review Board
ISF	Investigator Site File
ITD	Intertriginous Dermatitis
LTFU	Lost To Follow-Up
LU	Leg Ulcer
MARSI	Medical Adhesive-Related Skin Injury
MASD	Moisture-Associated Skin Damage

Abbreviation	Definition
MedDRA	Dictionary for Medical Drug Regulatory Activities
MVP	Moisture Vapor Permeable
NPUAP	National Pressure Ulcer Advisory Panel
PMS	Post-Marketing Surveillance
PP	Per-Protocol set
PSDL	Physical Symptoms of Daily Living
PU	Pressure Ulcer
QoL	Quality of Life
RCT	Randomized Clinical Trial
SADE	Serious Adverse Device Effect(s)
SAE	Serious Adverse Event(s)
SAF	Safety Analysis Set
SAP	Statistical Analysis Plan
SAS	Statistical Analysis System Software, Cary, NC, USA
SC	Standard Care
SL	Social Life
S&N	Smith & Nephew Inc.
SOP	Standard Operating Procedure
SQ	Satisfaction with Quality of Life
UADE	Unanticipated Adverse Device Effect(s)
USADE	Unanticipated Serious Adverse Device Effect(s)
VLU	Venous Leg Ulcer
WB	Well Being

## **4. INTRODUCTION**

### **4.1 BACKGROUND**

Chronic wounds, including leg ulcers (LU), diabetic foot ulcers (DFU), and pressure ulcers (PU), significantly impact patients' quality of life. These chronic wounds fail to heal and remain stuck in an inflammatory phase. In developed countries, the incidence of chronic wounds has increased in recent years, possibly due to an aging population with an abundance of concurrent illnesses such as diabetes, hypertension, obesity, and peripheral vascular disease.

In the United Kingdom, it is estimated that 15 to 18 out of 1000 people suffer from VLU; the cost to treat these and other chronic wounds was between £2-3 billion in 2006. More recent estimates put the annual cost of treating chronic wounds in the US at \$6-15 billion, however, a 2010 report puts the cost of treating DFU alone at \$39 billion.

Closure of complex wounds, including chronic wounds, post-surgical wounds, and trauma wounds is often achieved through secondary intention. Although these wound types have different etiologies and underlying pathophysiology, their treatment follows a similar course. Wound closure by secondary intention can be supported by a wide range of wound dressings designed specifically for this purpose. An ideal dressing must provide the following at a minimum:

- a barrier to exogenous contamination and infection
- adequate management of wound exudate
- maintenance of a moist wound healing environment

Failure of a dressing to deliver these fundamental features will negatively impact the ability of a complex wound to heal and may allow the wound to deteriorate. Failure to prevent contamination may allow a wound to become infected. Inability to manage moderate to high exudate volume may lead to maceration of the peri-wound skin, which can lead to further wound breakdown if untreated. At the same time, a dressing should not allow a wound to dry out; the dressing should maintain a moist wound healing environment. The consequences of wound

deterioration vary, but can result in protracted wound healing or may cause an otherwise preventable hospital episode for surgical management or closure.

This study will focus on the use of ALLEVYN LIFE™ Non-Bordered (ALNB) in the treatment of chronic wounds. ALNB is a new multilayer foam dressing that is intended to provide an optimal moist wound healing environment to promote the healing of moderate and highly exuding wounds.

ALNB is the latest addition to the ALLEVYN LIFE range of dressings, which were first launched in 2012. The introduction of ALNB recognizes the fact that clinicians sometimes prefer using a non-bordered absorbent product with wounds that require a secondary dressing, e.g. compression bandaging for leg ulcers.

While the present study will be the first clinical trial to evaluate the actual use of ALNB in clinical practice, the original ALLEVYN LIFE dressing has been used in several clinical studies. The results of these suggest that ALLEVYN LIFE supports good wound progression, wound granulation, healthy condition of the surrounding skin, and patient satisfaction.

Because medical devices are designed to improve the patient's quality of life, the primary outcome in the study will be the differences in Health-Related Quality of Life (HRQoL) between subjects treated with ALNB and Standard Care (SC) for subjects with moderate to highly exuding chronic wounds. The subjects will be surveyed using the Cardiff Wound Impact Schedule (CWIS) which measures the impact of chronic wounds on physical symptoms, daily living, social life, and well-being.

A summary of known and potential risks and benefits to humans of the test article can be found in the Package Insert (ALLEVYN LIFE Non-Bordered).

#### **4.2 SAFETY CONSIDERATIONS**

Precautions for the use of ALNB, as specified in the current Instructions for Use (IFU), are:

- Do not use with oxidizing agents such as hypochlorite solutions (e.g. EUSOL) or hydrogen peroxide, as these can reduce the absorbency of the dressing.

- If reddening or sensitization occurs discontinue use.
- Single-use only; if used on more than one subject, cross contamination or infection may occur.
- Once the pouch is opened, do not retain unused dressings for application at a later date.

Risks associated with the use of ALNB within the present study will be mitigated as follows:

- Study personnel will be trained in the correct use of ALNB prior to applying the dressing to the wounds of study subjects.
- Study personnel will be trained on the study protocol.
- Study personnel will be directed to carefully follow the inclusion and exclusion criteria for participation in the study when assessing the subject eligibility.
- Study personnel will be directed to read and follow the IFU.

#### **4.2.1 Benefits**

ALNB is a multilayer dressing with a silicone gel adhesive that provides an optimal moist wound healing environment to promote the healing of moderate and highly exuding wounds.

The absorbent pad is composed of a foam layer and a lock-away core made from superabsorbent material. The silicone adhesive layer is gentle, even to fragile skin, and makes it easy to apply, reposition, and remove. A breathable opaque outer film helps mask exudate, prevent bacterial contamination, and is showerproof when used with appropriate secondary retention.

#### **4.2.2 Hazards/Harms**

This will be the first study to evaluate the use of ALNB in clinical practice; there is currently no direct clinical evidence concerning the safety of ALNB.

ALLEVYN LIFE has been used widely over the last four years and has been shown to be equivalent to ALNB with regard to materials and fluid handling properties (see Section 6).

Published clinical studies with ALLEVYN LIFE, risk management reports, and post-marketing

surveillance (PMS) data consistently indicate that the risk of adverse events is low and that reactions which do occur are generally local to the application site and are mild in severity. Adverse events are well characterized and are manageable in the majority of cases. As such, ALLEVYN LIFE demonstrates an acceptable benefit-risk profile.

Because of the similarities between ALLEVYN LIFE and ALNB, the anticipated medical benefits of ALNB are also expected to outweigh risks. There are some differences between the two products, including:

- ALNB can be cut to size without compromising its performance characteristics
- ALNB does not incorporate a change indicator, as this would be obscured by any secondary dressing
- ALNB includes a lower tack adhesive, to serve as a ‘third hand’, and enable the dressing to be removed and repositioned more easily
- ALNB requires the use of a secondary dressing to aid retention

The use of a lower tack adhesive with ALNB may positively impact safety by lowering the incidence and severity of skin stripping resulting from its use. Unlike ALLEVYN LIFE, ALNB requires a secondary dressing to aid retention. Choice of ancillary dressing, together with associated risks relating to this secondary device, will be carefully monitored during this study.

There are no anticipated Serious Adverse Device Effects (SADE) associated with the use of ALNB.

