### 6.1.3 Ancillary Product

At Smith & Nephew's discretion, the following ancillary products may be made available to research sites for use on study subjects during this study – OPSITE™, PROFORE™, DURAFIBER™, and INTRASITE™. However, this study does not require any particular ancillary dressing to be used to secure ALNB. Rather, selection of ancillary dressings should be determined based on clinical requirements.

Per the IFU, physicians may use INTRASITE under ALNB, as clinically warranted.

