### **12.1.2 Adverse Device Effect (ADE)**

An Adverse Device Effect (ADE) is an adverse event that, in the opinion of the Investigator, is related to the investigational or comparator device:

- **Not Related** – An AE is considered to be not related to the use of the test article when the effect is DEFINITELY UNRELATED or UNLIKELY to have any relationship to the use of the test article;
- **Related** – An AE is considered to be related to the use of the test article when there is a POSSIBLE, PROBABLE, or DEFINITE relationship between the AE and the use of the test article.

AE related to the use of S&N ancillary products will be reported as ADE.

An ADE is further categorized depending on whether the criteria in section 12.1.3 and 12.1.4 are met.

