### **12.2 REPORTING PROCEDURES**

[figure not shown]
AE of any kind and DevD will be recorded in the applicable forms, eCRF, and source notes. The Investigator will evaluate all AE for relationship to the device, seriousness, and severity. ADE, SAE, and DevD will be entered into the eCRF and reported to the Sponsor within 24 hours of the Investigator being informed about the event (Figure 12.2-1). Updates to submitted information

will be recorded in the eCRF within 24 hours of the information being available to the Investigator. Ensure that for a device that causes an ADE/DevD, that the device information (Product Name, Product Code, Lot #, Expiration Date, and Size) are entered in the eCRF.

All SAE and ADE will be reviewed by a medically qualified person appointed by the Sponsor to determine which, if any, meet criteria for expedited reporting to the regulatory authorities.

The Investigator will inform the IRB of adverse events according to the IRB requirements.

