7.13 Analysis of Safety Endpoints

All safety analyses and summaries will be conducted using the Safety Population. Unless otherwise stated, all safety summaries will be presented by treatment and overall.

Extent of Exposure

The duration of treatment will be summarized by treatment and overall using descriptive summary characteristics for continuous data.

Adverse Events

Adverse events will be coded and grouped by system organ class using a recent version of the Dictionary for Medical Drug Regulatory Activities (MedDRA).

The number of subjects reporting: adverse events, serious adverse events, severe adverse events, device-related adverse events, serious device-related adverse events, unexpected adverse events, and serious unexpected adverse events will be summarized. In addition, for each adverse event, the following will be summarized: severity, treatment, the relationship to the investigational device, outcome and duration of the resolved adverse events and the duration of the adverse events at trial discontinuation.

The proportion of subjects with a device-related adverse event will be compared between treatments using Fisher's exact test.

The number and proportion of subjects reporting treatment-related adverse, by system organ class and preferred term will be summarized by treatment and overall for:

CONFIDENTIAL AND PROPRIETARY

This document contains information that is confidential and proprietary to Smith & Nephew PLC and Smith & Nephew, Inc. and is intended for use only by Smith & Nephew and its manufacturer. It shall not be reproduced or copied in whole or in part, nor shall the contents be disclosed by any means without prior written permission from Smith & Nephew, nor shall anyone make any use of it that is contrary to the expressed or implied wishes of Smith & Nephew

Statistical Analysis Plan	 Number: CT1603ALF ST: 1005 Version: 1.0, 27-Jul-2018 Page: 26 of 27
A Pilot Randomized Controlled Trial to Evaluate an Advanced Borderless Dressing (ALLEVYN™ LIFE Non-Bordered) in the Treatment of Chronic Ulcers	

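### A non-serious event blamed solely on the secondary dressing that ALNB requires is expressly device-related only if the product is the sponsor's, and no SAP safety summary covers such events

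*Protocol*

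**What the plan says.** **The promise.** Protocol 4.2.2 (Hazards/Harms) lists among the differences from the earlier product that "ALNB requires the use of a secondary dressing to aid retention". It continues: "Choice of ancillary dressing, together with associated risks relating to this secondary device, will be carefully monitored during this study". The commitment is not limited by manufacturer.

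**The products.** Protocol 6.1.3 states that "this study does not require any particular ancillary dressing to be used to secure ALNB". Four sponsor brands are named, but their supply is at the sponsor's discretion: "the following ancillary products may be made available to research sites for use on study subjects during this study".

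**The classification.** Protocol 12.1.2 defines an ADE as an event that, in the investigator's opinion, "is related to the investigational or comparator device". A possible relationship to use of the test article is enough. One sentence extends the definition: "AE related to the use of S&N ancillary products will be reported as ADE". Other makers' ancillary products are not mentioned.

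**The reporting.** Protocol 12.2 requires AEs of any kind to be recorded. The fast route is narrower: "ADE, SAE, and DevD will be entered into the eCRF and reported to the Sponsor within 24 hours" of the investigator learning of the event.

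**The analysis.** SAP 7.13 states: "The proportion of subjects with a device-related adverse event will be compared between treatments", using Fisher's exact test. The AE flags in SAP 7.4 and the relationship table in SAP 7.13 refer to the investigational device. Neither section mentions ancillary products.

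**The concern.** Retention is part of using ALNB, so a patient treated with it is exposed to ALNB plus a film, tape, bandage or compression system. A skin injury that the investigator blames only on that second product is expressly an ADE if the sponsor made it. If another company made it, nothing in 12.1.2 makes it an ADE. The injury and the reason for exposure are the same in both cases; only the maker differs. Which case applies depends on what a site stocks and whether the sponsor chose to supply it.

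At stake is the device-related tally in what 4.2.2 describes as the first clinical study of ALNB, with no direct clinical safety evidence before it. Section 8.3 justifies the 25 ALNB subjects by the need for basic safety data. Section 4.2.2 also suggests that the lower-tack adhesive may reduce skin stripping. A device-related count that can omit the product now doing the retention is a weak basis for judging that.

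**Working it through.** **1. No figure to reproduce.** The plan states no event rate or precision for this outcome. The arm sizes check: 40 × 5/8 = 25 ALNB and 40 × 3/8 = 15 SC.

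**2. Following one event through the rules.** Take a non-serious event with no device deficiency.

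| Attribution by the investigator | ADE under Protocol 12.1.2? | 24-hour list (12.2)? | In the SAP device-related tally? |
|---|---|---|---|
| ALNB at least possibly involved, any brand of retention | Yes | Yes | Yes |
| Solely an S&N secondary product | Yes, expressly | Yes | Unclear: SAP flag is for the investigational device |
| Solely another maker's secondary product | Not expressly | No | No provision |
| SC protective dressing, any brand (comparator, 6.1.2) | Yes | Yes | Unclear, for the same reason |
| SC arm, another maker's compression bandage | Not expressly, unless regarded as part of the comparator | No, on that reading | No provision |

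Rows 2 and 3 differ only by manufacturer. That conflicts with the unrestricted promise in 4.2.2. Rows 2 and 4 show a second mismatch: 12.1.2 includes comparator devices and S&N ancillaries, while the SAP flag names neither.

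**3. Whether other planned data fill the gap.**
- Protocol 9.2.2 to 9.2.4 record the brand of all dressings used, and SAP 7.11 summarises the type of secondary dressing as resource use. This shows what was applied, not which component was blamed for an event.
- Protocol 12.2 requires product details for a device that causes an ADE or device deficiency. A row 3 event is not expressly an ADE, so it does not clearly trigger this.
- Protocol 10.3 plans to summarise the possible cause of an event if it is related. The corresponding list in SAP 7.13 omits that item, and SAP 7.15 does not list the omission as a change. It would not reach an event classed as unrelated in any case.

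**4. Weight of one subject.** In the ALNB arm, 1/25 = 4 percentage points. In the SC arm, 1/15 = 6.7 percentage points.

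**5. Number of events at issue.** Let r be the proportion of ALNB subjects with an event blamed solely on the secondary product, and s the share of those products not made by the sponsor. The expected number outside the express ADE definition is 25 × r × s. The documents give neither input. Assuming r from 4% to 20% and s from 0 to 100%, the result runs from 0 to 25 × 0.20 × 1.00 = 5 subjects. That range is too wide to serve as an estimate.

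**6. Sensitivity of the Fisher test (hypothetical counts, two-sided p).**

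| Scenario | ALNB | SC | p |
|---|---|---|---|
| A. All events counted | 8/25 | 0/15 | 0.016 |
| A. Two ALNB events not counted | 6/25 | 0/15 | 0.067 |
| A. Four ALNB events not counted | 4/25 | 0/15 | 0.278 |
| B. All events counted | 8/25 | 2/15 | 0.269 |
| B. One SC event not counted | 8/25 | 1/15 | 0.117 |
| B. Both SC events not counted | 8/25 | 0/15 | 0.016 |

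Scenario A is what happens if the omissions fall in the ALNB arm. Scenario B is what happens if they fall in the SC arm, through another maker's ancillary product or because the SAP flag leaves out comparator events. A few classification decisions can move the comparison either way.

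**The case against.** **A possible link is enough.** Step 6 of the instructions for use (Protocol 21.1) makes secondary retention part of applying ALNB. An investigator could reasonably rate a skin event under the whole assembly as possibly related to use of the test article, and it would then be an ADE whatever the brand. This stands. It confines the gap to events blamed solely on the secondary product.

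**Nothing is lost from the database.** All AEs are recorded. Device deficiencies, which 12.1.6 defines without a brand limit, go on the 24-hour list, as do SAEs. This also stands. A reader might infer that harm with ALNB is undercounted overall; the documents support only that the device-related subset may be.

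**The direction is not shown.** A reader might infer that the rule favours ALNB, because SC may be any protective dressing, so injury from its adhesive border counts while injury from ALNB's separate retention may not. The documents do not support that conclusion. An injury from an SC dressing's own border is correctly attributed to the comparator. The S&N sentence is not specific to one arm, and ancillary and compression products may be used in both. If the SAP flag is taken literally, comparator events may not count at all, which would work against ALNB.

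**A recording field may exist.** The CRF and table shells are separate documents (SAP 2) and are not available here. The fair statement is that the protocol and SAP describe no component attribution.

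**Pilot status.** Section 5.6 expects no significant differences, and SAP 7.8 makes no multiplicity adjustment. That lowers the weight of the Fisher p-value. It does not excuse a classification rule at odds with the stated monitoring commitment.

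**Conclusion.** The point holds in a limited form. Protocol 4.2.2 promises monitoring of the secondary dressing's risks without regard to brand. Section 12.1.2 makes ADE status for an event due solely to that product express only for the sponsor's brand, and the SAP describes no analysis that delivers the promise. The device-related tally and its Fisher test may miss such events according to what a site uses. Non-serious events of this kind without a device deficiency also fall outside the 24-hour list.

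This rests on the text alone. The size does not: each reclassified ALNB subject is worth 4 percentage points, but how many there would be, and the net effect between arms, cannot be derived from the documents. The Fisher figures above are hypothetical and show only how sensitive a comparison of 25 with 15 is. The change is worth making because it is cheap and removes a rule that depends on the manufacturer.

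**What to change.** 1. **Protocol 12.1.2:** replace the sponsor-only sentence with a rule for ancillary products that is independent of manufacturer and identical in both arms.
2. **eCRF:** for each AE, record the component blamed: primary dressing, secondary retention, under-dressing product, or compression.
3. **SAP 7.4 and 7.13:** state that device-related covers the investigational or comparator device, in line with 12.1.2, and say how ancillary-related events are handled.
4. **SAP 7.13:** keep the Fisher comparison for the primary dressing and add a supplementary row, by arm, for events related to any part of the dressing system. Making the whole-system count the main comparison is debatable, since it would mix tape and compression injury into the device rate.

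The cost is a wording change in each document, one eCRF field, one table row, a few more 24-hour reports, and possibly a slightly higher device-related rate.
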